8.3. Tertiary/Exploratory Efficacy Analysis

Plasma biomarkers will be analyzed with the MMRM analysis as described above.

8.4. Subgroup Analyses of Efficacy Variables

The co-primary endpoints and iADRS will be analyzed by baseline severity, with subgroups defined as screening MMSE ≥ 21 and ≤ 27 versus MMSE < 21 . An additional subgroup analysis for the co-primary endpoints and the iADRS will use screening MMSE ≥ 20 and ≤ 27 versus

MMSE < 20. For these analyses, an MMRM model as previously described will be used, except that the model will have additional fixed effects for subgroup and its two-way interactions with treatment and Visit, and the 3-way subgroup-by-treatment-by-Visit interaction; and, baseline scores for the endpoint being analyzed and baseline MMSE and their interactions with Visit will be removed from the model due to their possible confounding with subgroup. Specifically, the analysis will include the categorical, fixed effects of treatment group, subgroup, pooled site, and Visit, along with the two-way interactions of treatment group with Visit and subgroup with Visit, and the three-way treatment group, subgroup, Visit interaction.

Similar models will be used to analyze subgroups by age (defined as < 65, 65-74 or ≥ 75), sex (defined as male or female), ethnicity (categories defined per FDA Guidance), ApoE4 genotype (defined as APOE4 non-carrier, carrier or homozygous) and medication use (cognitive enhancers, defined as yes or no).

There will be two additional subgroup analyses for the NPI-10. The first will include participants with a baseline NPI-10 score ≥ 2. The second will analyze the agitation/aggression domain scores in participants with a non-zero baseline score in that domain.

Note that there will be two sets of results for the mild subgroup. In section 8.2 the mild subgroup analyses are conducted by applying the primary analysis model to the ITT-mild analysis set. Those analyses are the primary means of drawing inference for the mild subgroup. The subgroup analyses described here for the mild / moderate subgroups are the primary means of drawing inference for differential efficacy between the subgroups. The analyses specified in section 8.2 are the primary means of understanding efficacy within the mild subgroup because that approach allows for including the same model as other secondary and primary endpoints.

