This document does not include the details of the planned analyses for the external Data Safety Monitoring Board (DSMB). The schedule of planned analyses is described in the DSMB charter and separate shells for tables, listings, and figures (TLF) are prepared for the DSMB meetings.

Descriptive summary tables for efficacy endpoints will generally include: number of participants with data, mean, standard deviation, median, 25% percentile, 50% percentile, 75% percentile, minimum and maximum. Inferential efficacy summary tables will include within group mean changes from baseline along with the difference between groups in mean change and the associated standard errors and p values.

Baseline is defined as the most recent non-missing measurement collected prior to the first dose.

2. Overall Study Design and Plan

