6.1.2. Adjustments for Covariates

Efficacy analyses will include as covariates the baseline value of the endpoint being analyzed and the MMSE baseline score, along with the interaction of these covariates with Visit. Investigative site (pooled, see section 6.1.6) will also be included as a categorical fixed effect.

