8.1. Co-Primary Efficacy Analysis

Visit wise mean changes from baseline will be analyzed in the ITT analysis set using a restricted maximum likelihood (REML)-based repeated measures approach (MMRM). The MMRM analysis assumes a missing at random (MAR) missing-data mechanism, meaning that drop out is related to observed outcomes of the dependent variable and covariates, but not to the unobserved outcomes. The analysis will include the categorical, fixed effects of treatment group, visit, and pooled site, along with the continuous, fixed covariates of baseline value of the endpoint being analyzed (baseline), baseline MMSE score, and the interactions of treatment group, baseline, and baseline MMSE with visit. An unstructured (co)variance structure will be used to model the within-participant errors. If this analysis fails to converge, the following structures will be tested in this order, with the first structure yielding convergence to be used as the appropriate structure for that variable: heterogeneous Toeplitz, heterogeneous compound symmetric, and compound symmetric. If one of the structures other than unstructured is used, variance of the Maximum Likelihood Estimator (MLE) will be based on the Sandwich Estimator (empirical option in PROC MIXED statement). If none of the structures yield convergence, site will be removed from the model and the sequence of covariance structures will be refit as described above. The Kenward-Roger approximation will be used to estimate denominator degrees of freedom.

Significance tests for the between-treatment group differences will use a two-sided 0.05 level, with the primary analysis based on the ITT analysis set.

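### The subgroup models in SAP 8.4 drop the endpoint baseline for a reason that does not touch the treatment contrasts: a small precision loss that wording alone can avoid

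*SAP*

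**What the plan says.** SAP 8.1 fits the co-primary MMRM with, among other terms, "baseline value of the endpoint being analyzed (baseline), baseline MMSE score, and the interactions of treatment group, baseline, and baseline MMSE with visit". SAP 6.1.2 sets the general rule: "Efficacy analyses will include as covariates the baseline value of the endpoint being analyzed and the MMSE baseline score", each also interacting with Visit.

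SAP 8.4 departs from this for the co-primary endpoints and the iADRS when subgroups are defined by screening MMSE, once with a cut at 21 and once at 20. There, "baseline scores for the endpoint being analyzed and baseline MMSE and their interactions with Visit will be removed from the model", and the reason is "due to their possible confounding with subgroup". The list of terms that follows contains no baseline term. On the purpose of these models, the same section says: "The subgroup analyses described here for the mild / moderate subgroups are the primary means of drawing inference for differential efficacy between the subgroups". Inference within the mild subgroup is assigned instead to the ITT-mild analyses of 8.2, whose MMRMs keep the covariates of the primary model.

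The next paragraph of 8.4 begins "Similar models will be used to analyze subgroups by age" and goes on to sex, ethnicity, ApoE4 genotype and cognitive-enhancer use. It names no covariates.

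**The concern.** The reason given and the stated purpose do not match. Differential efficacy is a treatment-by-subgroup contrast. Confounding with subgroup is a problem for comparing mild with moderate participants. It is not a problem for comparing randomised arms inside each subgroup, nor for the difference between those two comparisons. If the endpoint baseline predicts change, removing it leaves more residual variance in a contrast that is already imprecise.

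The second part is scope. Read straight on from the term list, the other subgroup models would be the same list with the subgroup factor exchanged, so both covariates would go there too. No reason is stated for those factors, and 6.1.2 has no exception for them. Two programmers could fit different models and each could point to the SAP.

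At stake are the width of the intervals for the subgroup contrasts and the reproducibility of the subgroup tables. No controlled claim is at stake.

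**Working it through.** **The plan's own figures (SAP 2.2).** Placebo change 5.0, SD 8.5, 45% difference, two-sided 0.05, 90% power.
- Difference: 0.45 × 5.0 = 2.25 points.
- n per group = 2 × (1.960 + 1.282)² × 8.5² / 2.25² = 300.
- With 20% drop-out: 300 / 0.8 = 375. Both stated figures reproduce.

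**Why the overlap does not reach the contrast.** With a common baseline slope b at a visit, the adjusted treatment effect in a subgroup equals the unadjusted effect minus b × (active minus placebo baseline mean in that subgroup). Randomisation makes the expected value of that bracket zero in each subgroup. At the 21 cut it is also stratified (SAP 2.4). The 20 cut is not a stratum, but it is still defined before randomisation. The expected contrast is therefore the same with or without baseline, whatever the correlation of baseline with subgroup.

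A Week 52 simulation confirms this: 804 randomised, about 20% missing at random, baseline strongly related to subgroup, true interaction −1.25, 4,000 trials per scenario. Endpoint baseline and MMSE were added together. The correlation is taken within subgroup.

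| Correlation of baseline with change | SE of subgroup main effect, without → with | SE of interaction, without → with |
|---|---|---|
| 0 | 0.96 → 1.49 | 1.361 → 1.363 |
| 0.3 | 0.96 → 1.42 | 1.361 → 1.301 |

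At 0.3 the mean interaction was −1.22 without and −1.23 with the covariates. The collinearity falls on the subgroup main effect only.

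**Size of the loss (complete data, 21 cut).** Inputs assumed, not in the documents:
- ρ: overall correlation of endpoint baseline with Week 52 change.
- Correlation of endpoint baseline with MMSE: −0.6.
- Half the participants mild, MMSE evenly spread, which gives a correlation of 0.866 between MMSE and the subgroup indicator.

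The correlation of baseline with subgroup is then r = 0.866 × 0.6 = 0.52 in absolute value, so r² = 0.27. The SD ratio of the interaction, without versus with baseline, is √[(1 − ρ²r²) / (1 − ρ²)]:
- ρ = 0: 1.000, no loss.
- ρ = 0.1: √(0.9973 / 0.99) = 1.004, a loss of 0.4%.
- ρ = 0.3: √(0.9757 / 0.91) = 1.035, a loss of 3.5%.
- ρ = 0.5: √(0.9325 / 0.75) = 1.115, a loss of 11.5%.

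For a baseline-MMSE correlation from −0.4 to −0.8, the loss runs from 4.3% to 2.5% at ρ = 0.3 and from 13.7% to 8.3% at ρ = 0.5. A five-visit MMRM simulation with about 20% random dropout gave the same order: 2.9% and 9.4% at the 21 cut, 3.7% and 10.2% at the 20 cut.

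**On the points scale.** Completers: 804 × 0.8 = 643, or about 160 per arm per subgroup with half mild. Taking 8.5 as the SD within subgroup, the 95% half-width without baseline is 1.96 × 8.5 × √(4/160) = 2.63 points. With baseline it is 2.63 / 1.035 = 2.54 (ρ = 0.3) or 2.63 / 1.115 = 2.36 (ρ = 0.5).

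**If the other subgroup models also drop baseline.** For a factor unrelated to baseline, r = 0 and the ratio is 1/√(1 − ρ²): 0.5%, 4.8% and 15.5% at ρ = 0.1, 0.3 and 0.5. The five-visit simulation gave 0.2%, 4.8% and 13.2%.

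**Where the SAP's reason does apply.** Adjusted arm-level means evaluated at the overall baseline mean would move by about ρ × 8.5 × r: 0.3 × 8.5 × 0.52 = 1.3 points, or 0.5 × 8.5 × 0.52 = 2.2 points, in opposite directions for mild and moderate. Both arms of a subgroup move equally, so the contrast is unchanged.

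**The case against.** The removal is pre-specified, reasoned and followed by a list of terms. For the severity models it is an explicit exception to 6.1.2, so a reader who infers an unresolved contradiction there goes too far. Both models are valid for the contrast, which makes the choice one of efficiency. This stands.

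The reason is not empty either. SAP Section 1 says inferential tables will show "within group mean changes from baseline along with the difference between groups in mean change", and arm-level means at a common baseline could mislead by the 1.3 to 2.2 points above. That also stands, but it concerns where the means are evaluated and does not require deleting the covariate. The mild/moderate time-savings analysis of 8.7 might be touched in the same way, though the SAP does not say that its means come from the 8.4 models.

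One could add that age or cognitive-enhancer use may also be associated with baseline severity. The SAP does not say so, and if it is true the same argument holds: the treatment contrasts are not confounded.

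A reader might infer that dropping baseline biases the subgroup results, because 8.1 rests on dropout where "drop out is related to observed outcomes of the dependent variable and covariates, but not to the unobserved outcomes", and 8.4 conditions on fewer covariates. Bias of that kind needs dropout to depend on baseline differently in the two arms. Nothing in the documents suggests that pattern. In a constructed one-arm scenario, the interaction differed between the two models by less than 0.1 point, against a half-width of about 2.6. The bias reading is not supported and the point does not need it.

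**Conclusion.** The point holds as a minor improvement. In the severity models, the stated reason does not justify removing the endpoint baseline for the contrast these models are meant to estimate, and the removal can only cost precision. Leaving MMSE itself out where MMSE defines the subgroup is not disputed. In the other subgroup models the natural reading is that both covariates are dropped as well, without a reason and against the general rule of 6.1.2. The text leaves this to inference.

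The loss is nil to about 3.5% in the SD of the interaction for ρ up to 0.3, and about 11.5% at ρ = 0.5. It depends on ρ, on the baseline-MMSE correlation and on the mild share, none of which the documents give. A reader might also infer a threat to the trial's main claims, and there is none: the co-primary analyses, the 8.2 ITT-mild analyses and the 6.1.3 hierarchy do not use these models.

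**What to change.** In SAP 8.4:

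1. Keep the endpoint baseline and its Visit interaction in all subgroup MMRMs.
2. Where MMSE does not define the subgroup, keep baseline MMSE and its Visit interaction too, in line with 6.1.2 and 8.1.
3. Evaluate arm-level LS means at each subgroup's own covariate means. This meets the concern behind the removal and leaves the treatment contrasts unchanged.
4. Replace the reference to similar models with the full list of terms for each subgroup factor. The present list also leaves out the treatment-by-subgroup term named just before it, and Section 13.2 plans tables by race although 8.4 names no race model.
5. Add to 6.1.2 that the MMSE-defined subgroup models omit baseline MMSE.

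The cost is SAP wording and one programming option for the LS means. No new data are needed, because the covariates are already collected and in the primary model. The endpoint baseline adds one slope per post-baseline visit (5 parameters), and MMSE adds 5 more where it is kept, with 804 randomised.

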8.5. Responder Analyses

A responder analysis will report the number and percentage of participants in each treatment group who remain stable or show improved scores on the co-primary endpoints (analyzed separately), baseline to week 52. These analyses will be conducted for all participants, and for the mild and moderate subgroups.

A second responder analysis for the NPI-10 will report the number and percentage of participants in each treatment group with a score of 0 at baseline and these numbers and percentages with a score of 0 again at week 52. This analysis will also be conducted for mild and moderate subgroups.

The significance of the difference between treatments in response rates will be assessed using the Cochran-Mantel-Haenszel (CMH) test in all participants, stratified by mild / moderate disease status; and the difference in response rates within disease subgroups will be assessed using the CMH test stratified by ApoE4 carrier status.

8.6. Disease Progression Analyses

A progression analysis will report the number and percentage of participants in each treatment group who entered the study with mild disease at baseline (MMSE 21-27) and who then progress to moderate or to more severe disease (MMSE 16-20 and MMSE <16, respectively) by week 52.

A second progression analysis will report the number and percentage of participants in each treatment group who entered the study with moderate disease at baseline (MMSE 16-20) and who then progressed to more severe disease (MMSE <16) by week 52.

The significance of the difference between treatments in the rate of disease progression will be assessed using the CMH test in all participants, stratified by mild / moderate disease status; and the difference in progression rate within disease subgroups will be assessed using the CMH test stratified by ApoE4 carrier status.

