4.2. Introduction

Data processing, tabulation of descriptive statistics, calculation of inferential statistics, and graphical representations will use SAS (release 9.4 or higher). If the use of other software is required, the final clinical study report will specify the software that was used.

In general, summaries will be provided by study treatment group, unless otherwise noted. The column headings for the summaries will include the randomized treatment groups (Placebo BID, Simufilam 100 mg BID), unless otherwise noted.

Continuous (quantitative) variable summaries will include the number of participants with non-missing values (n), mean, 2-sided 95% confidence interval (CI), standard deviation (SD) and/or standard error (SE) if applicable, median, and minimum and maximum values.

Categorical (qualitative) variable summaries will include the frequency and percentage of participants who are in the category for each possible value. In general, the denominator for the percentage calculation will be based upon the total number of participants in the study population for the treatment groups (or cohorts) unless otherwise specified.

The minimum and maximum will be reported with the same degree of precision (i.e., the same number of decimal places) as the observed data. Measures of location (mean and median) and bounds of CIs will be reported to 1 degree of precision more than the observed data and measures of spread (SD and SE) will be reported to 2 degrees of precision more than the observed data. Percentages will be presented to 1 decimal place.

Statistical testing and inference methods for safety and efficacy analyses are described below. Efficacy results will be considered statistically significant after consideration of the strategy for controlling the Type 1 error as described in Section 6.1.2 of this SAP. Nominal p-values may be computed for other efficacy analyses as a measure of the association between the endpoint and the treatment effect rather than formal tests of hypotheses. Unless otherwise stated, all statistical tests will be conducted at the $\alpha = 0.05$ (two-sided) level, and a difference resulting in a p-value of ≤ 0.05 will be considered statistically significant. Corresponding 95% two-sided CIs will be presented for statistical tests.

All formal statistical comparisons will be based on LS means from the relevant contrasts in the mixed model for repeated measurements (MMRM) or analysis of covariance (ANCOVA).

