4.3. Interim Analysis and Data Monitoring

No interim efficacy analyses or sample size re-estimations were conducted.

An external DSMB will be involved in the management of this study. The DSMB meeting will be held periodically for the duration of the study. The purpose of the DSMB is to review the progress of the study with special regard to safety and make recommendations to the Sponsor on how to handle any safety concerns that arise. Further details regarding the DSMB can be found in the DSMB charter which was finalized before the first meeting was scheduled.

5. Analysis Populations

The following analysis sets are planned for this study:

- **Intent-To-Treat (ITT) Analysis Set:** The ITT analysis set includes all randomized participants. The primary efficacy analysis will be based on this analysis set.
- **Intent-To-Treat (ITT-mild) Analysis Set:** The ITT-mild analysis set includes all randomized participants who have a baseline MMSE of 21-27.
- **Safety Analysis Set (SAF):** The SAF analysis set includes all participants who received at least one dose of study treatment. All safety analyses will be completed in the SAF analysis set and participants will be included in the group based on the treatment received.
- **PK sub-study Analysis Set:** The PK sub-study analysis set includes all participants who sign the PK consent and/or re-consent form and have at least one non-missing post baseline PK assessment available.

Assignment of participants to analysis sets will be confirmed at a blinded data review meeting to be held before the study database is locked.

6. General Issues for Statistical Analysis

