14.2.7.2.3	ITT	Summary of Change from Baseline to Week 52 in NPI Total Score By Visit and Treatment Stratified by Mild (20-27)/Moderate (<20) AD Status : Responder Analysis
14.2.8.1	ITT	Summary of Change from Baseline to Week 52 in Zarit Burden Index By Visit and Treatment
14.2.8.2	ITT-mild	Summary of Change from Baseline to Week 52 in Zarit Burden Index By Visit and Treatment
14.2.9.1	ITT	Summary of Change from Baseline to Week 52 in P-tau 217 By Visit and Treatment
14.2.10.1	ITT	Summary of Change from Baseline to Week 52 in GFAP By Visit and Treatment
14.2.11.1	ITT	Summary of Change from Baseline to Week 52 in NfL by Visit and Treatment
14.2.12.1	ITT	Summary of Change from Baseline to Week 52 in Total Tau by Visit and Treatment

Table Number	Population	Table Title/Summary
14.2.13.1	ITT	Summary of Individuals Entering the Study with Mild (MMSE:21-27) Alzheimer's Disease (AD) and Progressed to Moderate (MMSE:16-20) or Severe (MMSE:<16) AD by Week 52
14.2.13.2	ITT	Summary of Individuals Entering the Study with Moderate (MMSE:16-20) Alzheimer's Disease and Progressed to Severe (Moderate:<16) AD by Week 52

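### SAP 8.5 and 8.6 give no rule for missing status, so the default ITT denominator counts participants with no qualifying score as non-responders and non-progressors

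*SAP*

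**What the plan says.** SAP 8.5 reports the number and percentage per arm "who remain stable or show improved scores on the co-primary endpoints (analyzed separately), baseline to week 52". It adds an NPI-10 version: a score of 0 at baseline and again at Week 52. SAP 8.6 reports those "who entered the study with mild disease at baseline (MMSE 21-27) and who then progress to moderate or to more severe disease" by Week 52, with a second count of moderate participants whose MMSE falls below 16.

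Both sections test the arms. For progression: "The significance of the difference between treatments in the rate of disease progression will be assessed using the CMH test in all participants", with mild and moderate disease as the strata. Section 8.5 uses the same test and strata, and both add tests within the mild and moderate subgroups.

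Neither section sets a denominator or says what to do with a missing score. The general rule is in SAP 4.2: "In general, the denominator for the percentage calculation will be based upon the total number of participants in the study population", by treatment group, unless otherwise specified. The responder and progression tables in SAP 13.2 are labelled ITT, and SAP Section 5 defines that set: "The ITT analysis set includes all randomized participants".

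SAP 6.1.4 treats data after withdrawal as missing. The MAR-based MMRM (8.1) and the copy-reference imputation (8.1.1) concern mean changes. Neither is extended to these binary outcomes.

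**The concern.** Under the default, a participant with no usable score is in the denominator and cannot be in the numerator. In 8.6 that makes a missing outcome a good one; in 8.5 it makes it a bad one. The same missing data therefore push the two analyses in opposite directions. If more participants leave the active arm, the drug looks better on progression and worse on response, with no drug effect at all.

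This fits poorly with the rest of the plan. The co-primary and secondary estimands (SAP 3.2.1.1 and 3.2.1.2) use a hypothetical strategy for early discontinuation, asking what would have been seen had the participant stayed. The death sensitivity analysis in 8.1.1 assigns the worst observed result, yet under the 8.6 default a participant who died with no qualifying MMSE would count as not having progressed. The SAP reports only four deaths, so that example shows inconsistency, not size.

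At stake are two sets of rates and p-values that might be read as support for the main result.

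**Working it through.** **The plan's own figure.** The documents give no figure for these analyses. The one related figure is the sample size (SAP 2.2). The effect is 0.45 × 5.0 = 2.25 points with SD 8.5, so n = 2 × (1.960 + 1.282)² × 8.5² / 2.25² ≈ 300 per group. Then 300 / (1 − 0.20) = 375. Both reproduce, which fixes the planning dropout at 20%; it is not given by arm.

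**Inputs from the SAP.** 804 randomized 1:1, taken as 402 per arm; two-sided 5% level; CMH with two strata.

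**Assumptions, because the documents give no figures.** True event rate p = 40% in both arms and strata (range 30% to 50%); dropout averaging 20% but split unequally; dropout unrelated to outcome. The share of mild participants (50% to 70%) has almost no influence on the pooled test.

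**Formula.** With dropout d and a share c of dropouts' events still captured, the reported rate is p × (1 − d + d × c). The rejection rate follows from the normal approximation to CMH.

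**Worked case, 25% active v 15% placebo.**
- c = 0: the rates are 0.40 × 0.75 = 30.0% and 0.40 × 0.85 = 34.0%. The standard error is √(2 × 0.32 × 0.68 / 402) = 0.0329, so z = 0.040 / 0.0329 = 1.22 and the test rejects 22.9% of the time.
- c = 0.5: the rates are 0.40 × 0.875 = 35.0% and 0.40 × 0.925 = 37.0%. The standard error is √(2 × 0.36 × 0.64 / 402) = 0.0339, so z = 0.020 / 0.0339 = 0.59 and the test rejects 9.1% of the time.

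**All splits, no drug effect, p = 40%.**

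| Dropout, active / placebo | Rates, none captured | Rejection | Rates, half captured | Rejection |
|---|---|---|---|---|
| 20% / 20% | 32.0% v 32.0% | 5.0% | 36.0% v 36.0% | 5.0% |
| 22.5% / 17.5% | 31.0% v 33.0% | 9.3% | 35.5% v 36.5% | 6.0% |
| 25% / 15% | 30.0% v 34.0% | 22.9% | 35.0% v 37.0% | 9.1% |
| 30% / 10% | 28.0% v 36.0% | 68.2% | 34.0% v 38.0% | 21.9% |

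Simulation of the CMH test (40,000 trials each) gave 5.1%, 9.4%, 22.9% and 68.4% with none captured, and 5.0%, 6.2%, 9.1% and 22.3% with half captured. For 25% v 15%, event rates of 30% and 50% give 16.9% and 30.4% with none captured, and 7.7% and 11.0% with half captured.

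**If missing records are left out of numerator and denominator**, rejection is 5.0% for every split (simulation 4.8% to 5.1%), provided dropout is unrelated to outcome.

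**The case against.** A reader might infer three stronger things, and the documents support none of them.

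*That anyone who leaves before Week 52 cannot be seen to progress.* Progression is counted by Week 52, not at Week 52, and MMSE is also taken at Week 28. Protocol 7.1.6 and Section 9 collect the scales at early termination unless done within 30 days, and SAP 4.2 maps early-termination data to scheduled visits for efficacy as well as safety. Section 6.1.5 drops an early-termination assessment falling in a window where that scale is not scheduled, but this follows the safety-window rules and the efficacy paragraph does not repeat it. Some dropouts can therefore count as progressors, so the half-captured columns matter. The Week 28 route does not help 8.5, which needs status at Week 52; there only a late early-termination score can serve.

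*That the SAP tells CMH to treat missing as no event.* The 4.2 sentence opens with a general qualifier and concerns percentages. It does not say which records enter the test. Running CMH on non-missing records fits the text equally well and holds 5% under the stated assumption. But the percentage and its p-value would then describe different participants.

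*That the trial's main conclusions are at risk.* These tests are outside the hierarchy in 6.1.3.

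It is also fair that the dropout splits and event rates are assumptions, that disposition by arm (SAP 7.1) would show an imbalance, and that counting dropouts as non-responders is a common convention that works against the arm with more dropout. The responder half is therefore weaker. None of this defends counting a missing MMSE as no progression.

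**Conclusion.** The point holds in limited form. The default percentage denominator makes participants with no qualifying score non-progressors in 8.6 and non-responders in 8.5, and so understates both rates: 32% instead of 40% with 20% dropout in each arm and no dropout's event captured. A false treatment difference needs two further conditions: unequal dropout, and a CMH test run on that same denominator, which the SAP leaves open.

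If both apply, with 402 per arm, a 40% event rate and 25% v 15% dropout, a nominal 5% test rejects about 9% of the time when half of the dropouts' events are captured and about 23% when none are. The second figure is the worst case for that split. Equal dropout leaves the test at 5%. The within-subgroup tests are smaller: with an assumed 60% mild share and none captured, the same split gives about 16% (mild) and 12% (moderate).

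The co-primary and hierarchical results are not affected. This should be corrected before unblinding, chiefly for 8.6, because leaving the denominator open allows it to be chosen after the results are known.

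**What to change.** In 8.6, and for consistency in 8.5:

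- State that missing status is not counted as no progression.
- Derive Week 52 status from scores multiply imputed under MAR within arm, and combine results over imputations. Use the visits at which each scale is collected: Weeks 28 and 52 for MMSE and NPI-10, all five post-baseline visits for ADAS-Cog12 and ADCS-ADL.
- Keep this separate from 8.1.1. That analysis is MNAR copy-reference: active-arm dropouts are imputed from the placebo model, and its example code expects five post-baseline values. It cannot be reused as it stands.
- As a supporting analysis, report rates and CMH in participants with a usable Week 52 score.
- State whether Week 28 and early-termination scores count toward progression by Week 52.
- Use the same denominator for the percentage and the CMH test.

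The cost is SAP wording and modest programming. The results would rely on MAR, an assumption the primary MMRM already makes through its likelihood, without imputation.

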2.2. Sample Size and Power

Planned enrollment was approximately seven hundred fifty (750) participants with mild-to-moderate AD dementia. The sample size was determined by a power analysis of ADAS-Cog using data from a similar population over 52 weeks. This analysis determined that group sizes of 300 are powered to show a 45% mean difference from placebo at 52 weeks with 90% power and a two-sided significance level of 0.05. The power calculation assumes a true mean change from baseline for placebo of 5.0 points and a standard deviation of 8.5 points. Assuming a drop-out of 20%, each treatment group should enroll approximately 375 participants. The final sample size was 804 randomized participants.

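### The MMSE-threshold progression tests in SAP 8.6 leave out the baseline MMSE score that largely decides who crosses the cut, and give up some power

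*SAP*

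**What the plan says.** SAP 8.6 defines progression by MMSE category. Mild entrants (21-27) progress if they reach 20 or lower by Week 52; moderate entrants (16-20) progress if they fall below 16. The overall test is described thus: "the rate of disease progression will be assessed using the CMH test in all participants, stratified by mild / moderate disease status". Within the mild and moderate subgroups the CMH test is stratified by ApoE4 carrier status alone.

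SAP 6.1.2 gives a general rule: "Efficacy analyses will include as covariates the baseline value of the endpoint being analyzed and the MMSE baseline score". The same sentence adds interactions of these covariates with Visit, and the next adds pooled site. Neither 8.6 nor 6.1.2 says how the rule applies to a CMH test. Where SAP 8.4 drops the baseline covariates from its subgroup models, it says so and gives a reason.

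The responder section, SAP 8.5, uses the same kind of test: "response rates will be assessed using the Cochran-Mantel-Haenszel (CMH) test in all participants, stratified by mild / moderate disease status". Its endpoints differ, however: no worsening on ADAS-Cog12 or ADCS-ADL, and an NPI-10 score of 0 at baseline and again at Week 52.

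**The concern.** A participant entering at MMSE 21 progresses with a 1-point drop, while one entering at 27 needs a 7-point drop. In the moderate group the required drop runs from 1 point (entry at 16) to 5 points (entry at 20). Distance to the cut is therefore a strong predictor of the outcome, known for everyone before treatment. The overall CMH uses it only through the mild/moderate split, and the within-subgroup CMH does not use it at all. A strong prognostic variable left out of a test of a binary outcome costs power. At stake is the sensitivity of a progression comparison that the SAP commits to testing and tabulating (Tables 14.2.13.1 and 14.2.13.2).

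**Working it through.** **The plan's own figure.** SAP 2.2 states no rate or power for the 8.6 tests; its only power statement is for ADAS-Cog: "group sizes of 300 are powered to show a 45% mean difference from placebo at 52 weeks". The other inputs given there are a two-sided alpha of 0.05, power of 90%, a placebo decline of 5.0 points and an SD of 8.5. The effect is 0.45 × 5.0 = 2.25 points, so n per arm = 2 × (1.960 + 1.282)² × 8.5² / 2.25² = 300. "Assuming a drop-out of 20%, each treatment group should enroll approximately 375 participants": 300 / 0.80 = 375. Both figures reproduce. "The final sample size was 804 randomized participants", so at 20% dropout about 804 × 0.80 / 2 = 321 per arm would have Week 52 data.

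**How far baseline MMSE drives progression.** Assume a mean MMSE change of -m with SD s. A participant who must drop k points to cross has probability Φ((m - (k - 0.5)) / s). With m = 2.5 and s = 3.5:
- entry at 21 (k = 1): Φ(2.0 / 3.5) = Φ(0.571) = 72%
- entry at 27 (k = 7): Φ(-4.0 / 3.5) = Φ(-1.143) = 13%

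That is (72 - 13) / 6, or about 10 percentage points per MMSE point inside one stratum. Other inputs give the same pattern: 69% to 7% for m = 2, s = 3, and 69% to 24% for m = 3, s = 5.

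**Power of the planned CMH against a baseline-adjusted test.** The simulation used 300 per arm and 1,500 trials per setting, with both tests run on the same data. Assumptions not in the documents: baseline MMSE uniform or peaked over 16-27, placebo decline 2 to 4 points, SD 3 to 5, slowing of 30% or 45%. The adjusted test is logistic regression on treatment and baseline MMSE, plus the mild/moderate factor for all participants. Results for uniform baseline and 45% slowing:

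| Decline / SD | All: planned CMH → adjusted | Mild: CMH by ApoE4 → adjusted |
|---|---|---|
| 2 / 3 | 66.5% → 75.5% | 41.1% → 51.1% |
| 3 / 3 | 95.3% → 97.9% | 75.2% → 84.2% |
| 3 / 4 | 85.3% → 88.1% | 60.3% → 66.9% |
| 3 / 5 | 70.0% → 73.1% | 45.2% → 48.7% |
| 4 / 4 | 98.2% → 99.1% | 84.1% → 88.5% |

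Over all settings, including 30% slowing and the peaked baseline, the gain runs from 0.9 to 10.0 points. It is smallest when the SD is large or when power is already near its ceiling. CMH stratified on individual MMSE scores gives power within about 1.5 points of the logistic model.

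**Type I error with no drug effect.** Planned CMH 3.9% to 5.3%; logistic 4.2% to 6.0%. The simulation standard error is √(0.05 × 0.95 / 1,500) = 0.6 points, so both are consistent with 5%.

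**Whether the same applies to 8.5.** With the SAP 2.2 figures and normal changes, ADAS-Cog12 responder rates are Φ(-5.0 / 8.5) = 27.8% on placebo and Φ(-2.75 / 8.5) = 37.3% on simufilam, with 70.0% power at 300 per arm. With an assumed baseline-change correlation of 0 to 0.3, adjusting for baseline changes power by -0.4 to +1.5 points, about simulation error.

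**The case against.** The strongest reply is that nothing important rests on these tests. SAP 4.2 bases formal comparisons on LS means from the MMRM or ANCOVA and treats other efficacy p-values as nominal, and the hierarchy in 6.1.3 does not contain progression. SAP 8.2 already analyses MMSE change with continuous baseline MMSE, in ITT and ITT-mild. CMH is valid under randomisation and needs no functional form. All of this stands. It lowers the priority, but it does not remove the gain available in a test that the SAP commits to.

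Four stronger readings are tempting, and the documents do not support them:
- **That 8.6 breaches 6.1.2.** The Visit interactions and pooled site show that 6.1.2 was written for the repeated-measures model. Applied literally, it would demand terms that a single-visit test cannot have. What is missing is a statement of scope.
- **That 8.5 has the same flaw.** Its endpoints are not MMSE cuts, the calculated ADAS-Cog12 gain is negligible, and for NPI-10 responders the baseline is 0 by definition.
- **That baseline severity is ignored throughout.** Mild/moderate status is itself a two-level split of baseline MMSE, so the overall test uses it coarsely. Only the within-subgroup tests have no such term.
- **That chance imbalance biases the result.** Suppose 60% of the 643 participants with Week 52 data are mild, about 193 per arm, with baseline uniform over 21-27 (SD 2). The standard error of the baseline difference is then 2 × √(2/193) = 0.20 points, worth about 2 percentage points of progression. With progression near 40%, the standard error of the arm difference is √(2 × 0.40 × 0.60 / 193) = 5 points. The shift is about 0.4 standard errors, ordinary sampling noise that the CMH test already reflects.

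**Conclusion.** The point holds for SAP 8.6 as a loss of efficiency in supportive, nominal tests. The direction is secure, because distance to the MMSE cut determines much of the outcome. The size, roughly 1 to 10 percentage points of power both overall and in the mild subgroup, rests on assumed MMSE decline, SD, baseline distribution and drug effect, none of which the documents give. There is no validity problem, and no confirmatory conclusion changes.

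**What to change.** In SAP 8.6, make the test of treatment one that includes baseline MMSE, by either route:
- logistic regression on treatment and continuous baseline MMSE, with the mild/moderate factor added for all participants because the distance to the cut restarts at 21. Report a standardised risk difference with 95% CI, since the covariate-adjusted odds ratio is not on the same footing as the CMH one; or
- CMH stratified on individual or finely grouped MMSE scores, which gives nearly the same power.

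Keep the planned CMH as supportive and leave 8.5 unchanged. In 6.1.2, state that the covariate rule covers the MMRM and ANCOVA models, and say whether the CMH analyses are exempt.

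The cost is a few sentences in the SAP and a few lines of code. Baseline MMSE is already collected at screening. The change has to be made before unblinding to count as pre-specified.
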